8.2. Research objectives

The study objectives are to evaluate, to the extent measurable in the available routinely collected data, indicators of HCPs' adherence to the RMMs in accordance with the abrocitinib SmPC, prescriber's brochure and DHPC, specifically:

- Indicators of adherence to performing laboratory tests of CBC, lipid panel, hepatitis B/C and TB screening prior to initiation of abrocitinib treatment,
- Indicators of adherence to performing laboratory tests of CBC and lipid panel at week 4 (± 2 week) after initiation of abrocitinib treatment,
- Indicators of adherence to consideration of risk factors for VTE, MACE, malignancy excluding NMSC, NMSC, and serious infection prior to treatment with abrocitinib,
- Indicators of adherence to avoid live attenuated vaccines immediately prior to and during treatment with abrocitinib,
- Indicators of adherence to contraindications for use during pregnancy,
- Indicators of adherence to contraindications for use among patients with severe hepatic impairment,
- Indicators of adherence to no use in patients aged < 12 years, and
- Indicators of adherence to recommended posology (estimated average daily dose).

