9.2. Setting

The study population will include patients with a dispensing of abrocitinib as recorded in routinely collected electronic secondary population data in Denmark, France, Sweden, Spain and Hungary between the study start (country-specific aRMM distribution [01 Mar 2022, Sweden; 09 Mar 2022, Denmark; 31 Jul 2022, France; 30 Jan 2023, Spain; 05 April 2024, Hungary]) and study end (December 2026). Details on the data sources are in Section 9.4). All participating countries have universal health care.

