9.2.1. Inclusion criteria

All patients with at least 1 dispensing of abrocitinib between study start (country-specific aRMM distribution [01 Mar 2022, Sweden; 09 Mar 2022, Denmark; 31 Jul 2022, France; 30 Jan 2023, Spain; 05 April 2024, Hungary]) and December 2026 in the participating databases will be eligible for inclusion in this study. The date of the first dispensing of abrocitinib will be the index date. Patients must meet the above inclusion criteria to be eligible for inclusion in the study.

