9.2.2. Exclusion criteria

There are no exclusion criteria in this study.

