3) The proportion of patients with evidence of having risk factors and the number of risk factors for VTE, MACE, malignancy excluding NMSC, NMSC, and serious infection (including age 65 years or older, estimated dose of >100 mg/day for patients ages 65 or older, history of atherosclerotic disease, malignancy, pregnancy, history of VTE, use of combined hormonal contraceptives or hormone replacement therapy, major surgery, inherited coagulation disorder, diabetes, history of serious or opportunistic infection, TB) within 6 months prior to initiation of treatment with abrocitinib

4) The count and proportion of patients with evidence of having received live attenuated vaccines (e.g., measles, mumps, rubella) 4 weeks prior to and during treatment with abrocitinib

5) The count and proportion (among all pregnant women identifiable in a given database) of women in whom pregnancy overlaps with abrocitinib use

6) The count and proportion patients identified with severe hepatic impairment up to 6 months prior to or during treatment with abrocitinib

7) The count and proportion of patients aged <12 years on the index date

PFIZER CONFIDENTIAL

Abrocitinib B7451085 NON-INTERVENTIONAL STUDY PROTOCOL Version 2.0, 23 May 2024 8) The count of proportion of patients with an estimated starting dose > 100mg/day, and a description of the duration of use (median and IQR)

All proportions will be reported with 95% CIs.

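### The live-vaccine indicator merges a fixed 28-day pre-treatment window with variable treatment time in one proportion, so it rises with time on treatment and cannot show which half of the objective was breached

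*Protocol*

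**What the plan says.** The objective in Protocol section 8.2 covers two periods: "Indicators of adherence to avoid live attenuated vaccines immediately prior to and during treatment with abrocitinib". Section 9.7.1, item 4, turns it into one measure, a single count and proportion of patients recorded as having "received live attenuated vaccines (e.g., measles, mumps, rubella) 4 weeks prior to and during treatment with abrocitinib".

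The pre-treatment window is therefore 4 weeks for every patient. The second window is however long the patient is treated. Under section 9.2.1 one dispensing is enough to enter, and "The date of the first dispensing of abrocitinib will be the index date". Section 9.2.2 adds that "There are no exclusion criteria in this study". No minimum, maximum or common follow-up time is stated.

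For categorical variables section 9.7.1 plans counts and proportions, and all proportions carry 95% CIs. It names no person-time rate and no risk at a fixed time. Duration of use is described (median and IQR) under item 8, without a link to item 4. Section 9.9 discusses under-recording of vaccines but not unequal observation time.

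**The concern.** The probability of at least one event grows with the time observed. If one group of users is treated for a month and another for a year, and vaccinators behave identically towards both, the second group shows a higher proportion. A reader would see worse adherence where there is only longer treatment. In one country the same can happen across the two interim reports and the final report, as users accumulate treatment time.

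The two windows also reflect different decisions: starting abrocitinib soon after a live vaccine, and giving a live vaccine to someone already on treatment. Section 7 says the evaluation should help show whether the risk minimisation programme needs amending. The two kinds of breach would call for different messages to prescribers, and one total cannot tell them apart.

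**Working it through.** **Setting the items side by side.** For laboratory tests, section 9.7.1 separates the periods: item 1 covers the 3 months before initiation, and item 2 covers week 4 (± 2 weeks) after it. Each has its own fixed window and its own proportion. Item 4 has one proportion over both periods, and its second period has no fixed length.

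**The plan's own figure.** The protocol gives no expected value or precision target for the vaccine indicator. Its only sample-size figure is for laboratory tests (section 9.5): n = 0.5 × 0.5 × 1.959964² / 0.05² = 384.15, rounded up to 385. It reproduces, and this point does not depend on it.

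**Inputs.**
- Pre-treatment window: 28 days (section 9.7.1, item 4).
- Time on treatment: not given. Assumed 1 to 36 months. The upper bound follows from the start dates in section 9.2.1 and study end in December 2026 (taken as 31 December); in Denmark, for example, it is 57.8 months.
- Live-vaccination rate r: not given. Assumed 0.5 to 5 per 100 person-years, constant before and during treatment.

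**Formula.** The probability of counting in item 4 is 1 − exp(−r·t), with t = 28/365.25 + months/12 years. For the pre-treatment part alone, t = 28/365.25 = 0.0767 years.

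**Worked case at r = 0.01 per year.**
- 1 month on treatment: t = 0.0767 + 0.0833 = 0.1600; 1 − exp(−0.001600) = 0.16%.
- 12 months on treatment: t = 0.0767 + 1 = 1.0767; 1 − exp(−0.010767) = 1.07%.

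The ratio is 1.07 / 0.16, about 6.7, with identical vaccination behaviour.

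**Range over the assumed inputs.**

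| Months on treatment | r = 0.5 per 100 | r = 1 per 100 | r = 2 per 100 | r = 5 per 100 | 28 days as share of observed time |
|---|---|---|---|---|---|
| 1 | 0.08% | 0.16% | 0.32% | 0.80% | 47.9% |
| 6 | 0.29% | 0.58% | 1.15% | 2.84% | 13.3% |
| 12 | 0.54% | 1.07% | 2.13% | 5.24% | 7.1% |
| 36 | 1.53% | 3.03% | 5.97% | 14.26% | 2.5% |
| Pre-treatment part alone | 0.04% | 0.08% | 0.15% | 0.38% | – |

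From 1 to 36 months, time on treatment alone moves the indicator about 18- to 19-fold at every assumed rate. The pre-treatment part, reported alone, stays the same whatever the time on treatment. The on-treatment part, expressed per person-year, equals the assumed rate at any duration.

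**Loss of the split.** Suppose 8 of 385 users have a recorded live vaccine. Item 4 gives 8/385 = 2.1% whether all 8 were vaccinated before initiation, all 8 during treatment, or 4 in each period.

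**The case against.** **The wording is ambiguous.** Item 4 joins the periods with *and*, while item 6 joins its periods with *or*. Item 4 could be meant as two figures. That is possible, but the text offers one count and one proportion and nowhere says they are reported apart.

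**The SAP will settle it.** Sections 9.3, 9.6 and 9.7.1 leave algorithms, lookbacks, table layouts and detailed methods to the SAP. It could split the row, and it is a natural place for the fix. But the choice of a proportion and its two windows are stated in the protocol, so the default is as described.

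**The proportion answers the objective.** Section 8.2 names both periods in one bullet, and the share of users with any breach is a legitimate summary of it. This stands for the total; the split is what is lost. The duration summary in item 8 gives context but cannot recover it.

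**The effect is small.** With 385 patients, a proportion of 2% has a 95% CI of about ± 1.4 points (1.96 × √(0.02 × 0.98 / 385)), so a duration effect of a few tenths of a point would lie inside sampling error. This is fair as to size. It does not help with the missing split.

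**Stronger readings that the protocol does not support.**
- A reader might infer that the indicator misleads comparisons between countries with different start dates. No comparative analysis is planned (section 9.5), and results are presented by country (section 9.7.1). Vaccine capture already limits such a reading: Table 2 shows none in Sweden, Hungary to be confirmed, and partial capture in Denmark and France.
- A reader might infer that nearly all events will fall on treatment. That needs durations and rates that the protocol does not give. For a patient treated 1 month, the 28-day window is 47.9% of the observed time.
- Scenarios in which nobody stops treatment before study end give larger distortions, but they are an extreme and should not set the expected size.

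**Conclusion.** The point holds as a matter of interpretation within each country. Read as written, item 4 yields a proportion that rises with time on treatment and does not separate the two periods that the objective names. The direction needs only that some vaccination occurs during treatment and that durations differ. The size is unknown. The illustration of 0.16% at 1 month against 1.07% at 12 months rests on an assumed constant rate of 1 per 100 person-years. Drift between reports is possible rather than certain, because new initiators with short treatment time offset the time accrued by existing users. Sample size and the 385 figure are unaffected. The under-recording acknowledged in section 9.9 is a separate limit that remains. This is a worthwhile, inexpensive improvement, not a flaw that invalidates the study.

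**What to change.** Replace item 4 with two indicators, in section 9.7.1 or in the SAP with the protocol aligned, each with a 95% CI:

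- (a) Count and proportion of all initiators with a recorded live attenuated vaccine in the 28 days before the index date.
- (b) Count and proportion with a recorded live attenuated vaccine during treatment, accompanied by either a rate per 100 person-years on treatment or a cumulative incidence at a stated fixed time, with censoring at the end of treatment or of data.

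The combined figure can stay as a total if wanted. The cost is one more table row and a person-time denominator. Vaccination dates and treatment periods are already needed for item 4 as it stands, so no new data are required. The change concerns reporting only and leaves the 4-week window as it is.

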Population The study population will include patients with a dispensing of abrocitinib as recorded in routinely collected electronic healthcare data in Denmark, France, Sweden, Spain and Hungary during the study period (study start: country-specific aRMM distribution [01

PFIZER CONFIDENTIAL

Abrocitinib B7451085 NON-INTERVENTIONAL STUDY PROTOCOL Version 2.0, 23 May 2024 March 2022, Sweden; 09 March 2022, Denmark; 31 July 2022, France; 30 Jan 2023, Spain; 05 April 2024, Hungary]; study end: December 2026). These countries have universal healthcare.

Variables The study will collect all relevant data including patient demographics, comorbidities, prescription medications, vaccine administration, and laboratory testing prior to the initiation of abrocitinib and during treatment with abrocitinib to address the study objectives.

Data sources This study will utilize routinely collected electronic healthcare data from national or regional population-based electronic healthcare registers in Denmark, Sweden, and Spain and an administrative healthcare databases in France and Hungary.

Study size All patients initiating abrocitinib during the study period will be included.

Data analysis Data will be analysed in each country separately using a common protocol, database-specific definitions of the study variable, and common analysis strategy. The main indicators will be proportions of abrocitinib users with a given indicator of aRMM adherence.

Milestones

Milestone	Planned date*
Registration in the HMA-EMA Catalogues of RWD Studies	To be registered before the start of data collection
Start of data collection	31 December 2024
End of data collection (the date from which the analytical dataset is completely available, i.e., clean and coded data from all participating countries/databases)	15 May 2028
Interim Report 1	15 November 2025
Interim Report 2	15 May 2027
Final study report	15 November 2028

* Subject to data delivery and application approval timelines by data custodians in participating countries

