9. RESEARCH METHODS

9.1. Study design

This will be a descriptive drug utilization study using secondary data from healthcare databases in Denmark, France, Sweden, Spain and Hungary. The study population will comprise patients who are treated with abrocitinib.

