9.5. Study size

There is no minimum sample size planned in this study. This is a descriptive study and no comparative analyses will be conducted. Thus, the purpose of the sample size calculations provided below is to describe the precision of the estimates.

The following formula, based on the normal approximation to the binomial proportion, was used to calculate the sample size for this study:

$$n = \frac{P \cdot (1-P) \cdot \left(Z_{1-\alpha/2}\right)^2}{e^2},$$

Where *P* is the expected proportion of patients with evidence of having performed the recommended laboratory test prior to/during treatment with abrocitinib (e.g., CBC); *e* is the margin of error, or half the desired width of the confidence interval (CI); and $Z_{1-\alpha/2}$ is the standard normal *Z*-score corresponding to a cumulative probability of $1-\alpha/2$.

As the proportion of patients with evidence of having performed the recommended laboratory test prior to/during treatment with abrocitinib (p) is not known in advance, it will be set to 50%, which yields the most conservative (i.e., the largest) sample size for a specified margin of error. Therefore, to obtain 95% CIs with a desired width of 10% (half width of 5%) for each laboratory test, the study will require a sample size of at least

385 patients. Note that the proportion of patients with evidence of having performed the laboratory test will vary by test which will affect the precision as well (Table 3).

Table 3.Number of Abrocitinib Treated Patients by Proportion of Patients With
Evidence of Having Performed the Recommended Laboratory Test and
Width of 95% CI

Proportion of patients with evidence of having performed the recommended laboratory test	Width of 95% CI	Required Number of Patients
25%	0.10	289
	0.15	129
	0.20	73
50%	0.10	385
	0.15	171
	0.20	97
75%	0.10	289
	0.15	129
	0.20	73

Although the sample size identified to meet the aforementioned precision estimate requirements is 385, the study will include all patients identified during the study period who meet the eligibility criteria to maximize the precision of the estimates.

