9.9. Limitations of the Research Methods

Given the use of data sources from 5 distinct EU countries in this study, there will be variability in data captured across the participating countries. For example, data on laboratory tests and vaccinations are not available in Sweden and may be underrecorded in Denmark and France. If only reimbursed services are recorded (e.g., vaccinations, oral contraceptives), some underascertainment will be associated with absence of data on nonreimbursed services. Given the underrecording, absence of a record of a given RMM metric (e.g., hepatitis B, hepatitis C, or TB screening) cannot be interpreted as an indicator of nonadherence for all metrics, and only databases with high completeness of these data should be used in that assessment (Table 2). Similarly, as vaccines recording is based on reimbursement and data is not expected to be complete, the absence of a record is not necessarily indicative of absence of vaccine receipt. Additionally, prescription strength data serves as a proxy for daily dosage in this study; this approach is supported by the absence of scoring on the abrocitinib 200 mg tablets (which would facilitate splitting into separate 100 mg doses), and by reimbursement in Sweden, Denmark, France and Spain (pending for Hungary) for both the 100 mg and 200 mg tablets (i.e. there is no financial justification for a patient to receive a prescription strength of 100 mg to be taken as 2 tablets to achieve 200 mg daily dosage). However, there may be instances where patient dosage does not correspond to the strength prescribed. Dosage data from SIDIAP can only be derived from a combination of WHO Defined Daily Dose (DDD); data from NHIFA on dosage is not available.

Other limitations include uncertainty about identification of abrocitinib in Denmark (however, most newly approved medicines receive hospital procedure codes); incomplete identification of ongoing pregnancies and pregnancies ending in a termination, as they are identifiable only by pregnancy end date; challenges in identifying screening for TB and hepatitis B and C in all participating countries; and potential underestimation of history of atherosclerotic disease given the likelihood of treatment within a primary care setting in all participating countries. Results from participating countries will not necessarily be generalizable to other countries in the EU.

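### The pregnancy indicator in Protocol Section 9.7.1 (item 5) is a proportion of all pregnant women in the database, not of women given abrocitinib, so the proportion does not measure adherence

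*Protocol*

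**What the plan says.** The objective in Protocol Section 8.2 is "Indicators of adherence to contraindications for use during pregnancy", listed among indicators of healthcare professionals' adherence. Section 9.7.1, item 5, turns this into "The count and proportion (among all pregnant women identifiable in a given database) of women in whom pregnancy overlaps with abrocitinib use". The same section adds: "All proportions will be reported with 95% CIs".

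Three other places set a different base:

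- Section 4 (Abstract, data analysis): "The main indicators will be proportions of abrocitinib users with a given indicator of aRMM adherence".
- Section 9.1: "The study population will comprise patients who are treated with abrocitinib". Section 9.2.1 requires at least one abrocitinib dispensing for inclusion.
- Section 9.7.1, item 6, on the other contraindication: "The count and proportion patients identified with severe hepatic impairment up to 6 months prior to or during treatment with abrocitinib". This is a proportion of study patients.

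**The concern.** Only women who receive abrocitinib can show whether the pregnancy contraindication was followed. Pregnant women who were never prescribed the drug carry no information on that question, yet they make up nearly all of the item 5 denominator. They are also outside the study population.

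The resulting proportion would be very small whether prescribers follow the contraindication well or badly. It would rise when more patients start the drug and fall when the database covers more pregnancies. A small percentage with a narrow confidence interval, reported under an adherence objective, invites a reassuring reading that it cannot support.

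**Working it through.** **The plan's own figure.** Section 9.5 uses n = P(1−P)z²/e². With P = 0.5, z = 1.96 and e = 0.05, n = 0.25 × 3.8415 / 0.0025 = 384.15, rounded up to 385. All nine cells of Table 3 reproduce. This calculation concerns laboratory tests; the protocol gives no precision figure for the pregnancy indicator. I use 385 below only as a reference number of treated patients. Section 9.5 sets no minimum and includes all users.

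**Structure of the indicator.** Let N be the number of female users, q the share of them pregnant while exposed, and D the number of pregnant women in the database. Item 5 reports N × q / D. Adherence is reflected in q alone. The factor N / D is uptake divided by the size of the pregnant population, and it caps the indicator even at q = 1.

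**Size of D.** D = population × pregnancies per inhabitant per year × years. Populations are from Section 9.4. Years run from the country start dates in Section 9.2 to 31 December 2026 (the protocol gives only the month). The pregnancy rate is an assumption, taken as 5 to 15 per 1,000 inhabitants per year, and pregnancies stand in for pregnant women. For Denmark at the low end, 5.8 million × 0.005 × 4.81 gives about 140,000.

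The last column is 385 / D, the extreme in which 385 women in that one country were all pregnant while exposed.

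| Country | Population | Years | D (5 to 15 per 1,000) | 385 exposed women |
|---|---|---|---|---|
| Denmark | 5.8 million | 4.81 | 140,000 to 419,000 | 0.28% to 0.09% |
| France | 67 million | 4.42 | 1.48 to 4.44 million | 0.026% to 0.009% |
| Sweden | 10.4 million | 4.84 | 251,000 to 754,000 | 0.15% to 0.05% |
| Spain | 5.8 million | 3.92 | 114,000 to 341,000 | 0.34% to 0.11% |
| Hungary | 9 million | 2.74 | 123,000 to 370,000 | 0.31% to 0.10% |

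With 2,000 exposed women in one country, the highest value would be 2,000 / 113,618 = 1.8% (Spain, low rate).

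**Comparison with a user-based denominator.** Assume 193 female users in a country (half of 385, rounded up), with Wilson 95% CIs:

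| Exposed women | Share of 193 female users (95% CI) | Item 5 proportion, range over countries and rates |
|---|---|---|
| 10 | 5.2% (2.8% to 9.3%) | 0.0002% to 0.009% |
| 96 | 49.7% (42.8% to 56.7%) | 0.002% to 0.08% |

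The user-based share separates good from very poor adherence. The item 5 proportion stays below 0.1% in both rows.

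**Dependence on uptake and database size.** If the number of users doubles at the same adherence, 20 of 386 are exposed instead of 10 of 193. The user-based share stays at 5.2%, while the item 5 proportion doubles. At 10 pregnancies per 1,000, the same ten exposed women give 0.0036% in Denmark (10 / 279,162) and 0.00034% in France (10 / 2,960,657), a ratio of 10.6 that comes from the size of the pregnant population alone.

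**The case against.** The strongest reply is that item 5 reports a count as well as a proportion. The count does not depend on the denominator, and Section 9.7.1 also reports the age and sex of users by country, so a reader could approximate a user-based share. That stands. One might infer from the near-zero proportion that the study cannot detect a failure of the contraindication at all; the protocol does not support this, because the count carries the signal. What remains is that the protocol gives the count no user-based denominator and attaches the 95% CI to the wrong proportion.

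Item 3 also lists pregnancy among patients' risk factors, but only within 6 months before initiation, so pregnancy during treatment is not covered there.

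The denominator could be read as pregnant women within the treated cohort. The reference to a given database does not fit that reading. Even if it were meant, the proportion would be conditional on pregnancy and would still not give the share of treated women who were exposed.

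Section 9.9 says that ongoing pregnancies and terminations are incompletely identified "as they are identifiable only by pregnancy end date". A reader might infer that exposed pregnancies still in progress in December 2026 are lost and that this always biases the indicator downwards. The protocol does not establish that. December 2026 bounds dispensing and eligibility, and nothing stops outcome ascertainment on that date. Section 6 puts the complete analytical dataset at 15 May 2028. Table 2 allows for a Danish algorithm for ongoing pregnancies and lists Spain without restriction. Any pregnancies missed at the end would also leave both numerator and denominator.

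Difficulty in comparing countries is a lesser harm, since results are presented by country and no comparative analysis is planned.

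**Conclusion.** The denominator of item 5 is wrong for its objective and conflicts with the abstract, Section 9.1 and item 6. It is written into the protocol, not left to the SAP, and no other section repairs it. The proportion and its 95% CI reflect drug uptake and the number of pregnancies in the database, not adherence.

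The conclusion that the proportion is near zero rests on the assumed 5 to 15 pregnancies per 1,000 inhabitants per year and on 385 as a reference size. It holds over that whole range, with a ceiling of about 0.34% for 385 exposed women in one country. The exact percentages are illustrations. The inconsistency between the sections does not depend on them.

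**What to change.** In Section 9.7.1, item 5, make the denominator women of childbearing age with at least one abrocitinib dispensing in the study period, with the age band stated in the SAP. Report the count of women whose pregnancy overlaps with use, and the proportion with 95% CI. Drop the proportion among all pregnant women, or keep it labelled as a secondary description.

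The cost is about one sentence in the protocol. The revised indicator uses dispensing, age and sex data that the study already collects, together with the pregnancy identification already planned. Section 9.7.1 says that major modifications are to be reflected in a protocol amendment, so the change belongs in the next amendment.

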The principal investigator institution (Aarhus University) will use the country-specific aggregate data supplied via the data template (using Microsoft Excel) to generate country-specific or combined output, as appropriate per planned Tables, Listings and Figures, which will be specified in the SAP.

Approaches to federated analysis (common data models and/or scripts) may be considered. The investigators will use either SAS or R software, in the most recent version available to their organisations at the time of the analyses.

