9.7. Data Analysis

9.7.1. Main analyses

Detailed methodology for summary and statistical analyses of data collected in this study will be documented in the SAP, which will be dated, filed, and maintained by the sponsor. The SAP may modify the plans outlined in the protocol; any major modifications would be reflected in a protocol amendment.

Data will be analysed in each country separately using a common protocol, database-specific definitions of the study variable, and common analysis strategies. Only data available in a given country will be analysed and presented (Table 1,Table 2). The results will be presented separately for each country.

For each country, patient baseline characteristics will be reported to the extent measured in each database, including demographics (age and sex), comorbidities (including asthma, food allergies, depression) and prior and current medication use (including treatments for atopic dermatitis and medications noted for interactions in the abrocitinib label as captured in outpatient dispensing data or other available secondary routinely collected data on medication use). Other characteristics frequently diagnosed among patients with atopic dermatitis may be added given acceptable validity and completeness measured via diagnoses or treatment proxies and known in time for inclusion in planned data extractions; existing

PFIZER CONFIDENTIAL

ethical and data protection permissions and the associated data applications may need to be amended to enable inclusion of additional variables.

Counts and proportions for categorical variables and mean, median with range or interquartile ranges (IQRs) for continuous variables will be reported to address the study objectives, as follows:

1) The count and proportion of patients with evidence of having performed the following laboratory tests and screenings within 3 months prior to initiation of abrocitinib:

- CBC including absolute lymphocyte count, absolute neutrophil count, platelet count and haemoglobin level
- Lipid panel (ie, total cholesterol, HDL, LDL, and TG)
- Screening for TB, and
- Screening for viral hepatitis B and C

2) The count and proportion of patients with evidence of having performed the following laboratory tests at week 4 (\pm 2 weeks) after initiation of abrocitinib:

- CBC including absolute lymphocyte count, neutrophil count, platelet count and haemoglobin level
- Lipid panel (i.e., total cholesterol, HDL, LDL, and TG)

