9.7.2. Sensitivity analyses

The main analyses will be repeated among patients with evidence of AD before abrocitinib initiation. An additional sensitivity analysis will be undertaken in which the date of study period start is aligned with the date of the SmPC issue (09 Dec 2021).

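### The only indicator for the severe hepatic impairment contraindication pools impairment before and during treatment, so it cannot distinguish use against the contraindication from new impairment followed by stopping

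*Protocol*

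**What the plan says.** Protocol section 8.2 lists as an objective "Indicators of adherence to contraindications for use among patients with severe hepatic impairment". Section 9.7.1 introduces its numbered list by saying that counts and proportions "will be reported to address the study objectives, as follows". The entry for this objective is item 6: "The count and proportion patients identified with severe hepatic impairment up to 6 months prior to or during treatment with abrocitinib".

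No other item covers hepatic impairment; it is not among the risk factors named in item 3. Section 9.7.2 plans two sensitivity analyses. In one, "The main analyses will be repeated among patients with evidence of AD before abrocitinib initiation"; the other moves the start of the study period to the SmPC date. The limitations in section 9.9 do not raise the timing of hepatic impairment.

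Several matters go to the SAP: variable algorithms and lookbacks (section 9.3), output "as appropriate per planned Tables, Listings and Figures, which will be specified in the SAP" (section 9.6), detailed methodology (section 9.7.1) and the code algorithm for severe hepatic impairment (Annex 3, Table A1). Section 9.7.1 adds: "The SAP may modify the plans outlined in the protocol; any major modifications would be reflected in a protocol amendment".

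**The concern.** The objective is about what prescribers do: whether abrocitinib is used in patients in whom it is contraindicated. Item 6 counts patients with a diagnosis in either of two windows, whatever the prescriber did next. New hepatic impairment during treatment is a clinical event, not a prescribing decision. The decision that bears on adherence is whether dispensing continues afterwards, and item 6 does not look at that.

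Section 7 says the evaluation should show whether the risk minimisation programme met its objectives or needs amending. For this contraindication, a reader of the single figure could not tell a failure to heed the warning from its correct application after a change in the patient's condition. Because the extra patients are only ever added to the numerator, the error runs towards overstating non-adherence among recorded cases.

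**Working it through.** **1. The protocol's own figure.** Section 9.5 uses n = P(1 − P)z²/e². With P = 0.50, z = 1.96 and e = 0.05, n = 0.25 × 3.8415 / 0.0025 = 384.15, rounded up to 385. This agrees with the text ("Although the sample size identified to meet the aforementioned precision estimate requirements is 385"). With e = 0.10, n = 96.04, rounded up to 97, as in Table 3. These are precision figures for laboratory tests. They serve below only as illustrative denominators, since the protocol gives no expected number of users per country.

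**2. Who enters the item 6 numerator.**

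| Patient | Counted in item 6? | Use against the contraindication? |
|---|---|---|
| Impairment recorded in the 6 months before the first dispensing, then started | Yes | Yes |
| Impairment first recorded on treatment, dispensed again afterwards | Yes | Yes, continued use |
| Impairment first recorded on treatment, not dispensed again | Yes | Not shown; compatible with correct stopping |

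**3. Whether another part of the plan separates them.** Item 3 omits hepatic impairment. The sensitivity analyses change the population or the start date, not this numerator. Elsewhere the list does fix timing: laboratory tests are split into before initiation (item 1) and week 4 (item 2), and age is taken on the index date (item 7). Item 4 also joins two periods, but a live vaccine given on treatment is itself contrary to the recommendation, so pooling does less harm there.

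**4. Effect of one patient who was newly impaired and then stopped.** Section 9.7.1 says "All proportions will be reported with 95% CIs" without naming a method, so exact (Clopper-Pearson) limits are assumed:
- x = 0: lower limit 0, upper limit 1 − 0.025^(1/n).
- x = 1: lower limit 1 − 0.975^(1/n), upper limit the 97.5th percentile of Beta(2, n − 1).

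| n | Without this patient | With this patient |
|---|---|---|
| 385 | 0/385 = 0% (0 to 0.954%) | 1/385 = 0.260% (0.007% to 1.439%) |
| 97 | 0/97 = 0% (0 to 3.732%) | 1/97 = 1.031% (0.026% to 5.610%) |

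**5. What a given result can mean.** Suppose item 6 flags 4 of 385 patients (an assumed count). The reported result is 4/385 = 1.04% (0.28% to 2.64%) whatever the mix.
- All four newly impaired and stopped: use against the contraindication is 0/385 = 0% (0 to 0.95%).
- Two of the four: 2/385 = 0.52% (0.06% to 1.86%).
- None of the four: 4/385 = 1.04% (0.28% to 2.64%).

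The same published figure fits all three.

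**6. Window length.** The window before treatment is 6 months. The window on treatment is limited only by each patient's use and the study end. From the start dates in section 9.2, the longest possible span is about 58 months in Sweden (March 2022 to December 2026) and about 33 months in Hungary (April 2024 to December 2026). These are maxima, not expected durations. They show that the pooled count can grow with time on treatment, and can differ between countries, with no difference in prescribing behaviour.

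**The case against.** The strongest reply is that this is tabulation detail for the SAP, which was not available for this review. Item 6 names both windows and does not forbid showing them separately, the SAP may modify the plan, and the necessary dates will be in the data. It is true that the SAP could add a split. But the deferrals cover code algorithms, lookbacks, table layouts and detailed methods. None calls for a split, and better codes or another lookback would not repair a numerator that mixes different behaviours.

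A second reply is that the objective concerns use, not only initiation, so the on-treatment period belongs in the indicator. That is right, and it is why the on-treatment period should be kept; what is missing is the condition on later dispensing.

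A third is that the study is descriptive, no threshold or test attaches to item 6, and the effect is small and hypothetical. That stands as a limit on severity. It does not make the figure interpretable.

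A fourth is that the split is imperfect: the first recorded code need not mark onset, case finding relies on proxies still being developed, and rare cases would be divided by country and by category. These points stand and are handled as caveats in the proposed change.

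**Conclusion.** The concern holds. As written, item 6 does not isolate adherence to the hepatic contraindication, and it can be above zero with no prescriber having started or continued abrocitinib in a patient with known severe impairment. Its size cannot be derived from the protocol and is probably small in absolute terms: one patient is 0.26 percentage points at 385 and 1.03 at 97, with widely overlapping intervals. What is at stake is mainly whether the count for a contraindication reads as zero or not. The illustration assumes exact intervals and borrows its denominators and case counts; the conclusion about the definition does not depend on them. The change should be made, but the study's other indicators are unaffected.

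**What to change.** In section 9.7.1, item 6, keep the pooled total and add three counts and proportions:

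- (i) severe hepatic impairment recorded in the 6 months before the index dispensing, as the main indicator of starting against the contraindication;
- (ii) impairment first recorded during treatment with at least one later abrocitinib dispensing, as an indicator of continued use;
- (iii) impairment first recorded during treatment with no later dispensing, reported separately and not read as non-adherence.

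Attach a caveat to (iii): absence of a later dispensing may reflect supply in hand or the end of the data, and some of these patients may have had unrecorded impairment at the start. In the illustration above, the single newly impaired and stopped patient falls in (iii), and (i) and (ii) stay at zero.

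The cost is one sentence in the protocol and table-shell wording in the SAP, using diagnosis and dispensing dates the study already needs. The drawback is small cells that may have to be suppressed in some countries, which is one reason to retain the pooled total.
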